### **9.1.2 Advanced Solid Malignancies**

For cohorts that have at least 5 subjects at the recommended Part B dose of 75 mg BID, the frequency of responders according to modified RECIST 1.1 criteria for subjects with advanced solid malignancies will be evaluated at each dose level. The changes from baseline in overall assessment of CR, PR, SD and PD will be reported. The frequency of disease assessment to treatment will be provided in a data listing by subject.

### **9.1.3 Myelofibrosis**

For cohorts that have at least 5 subjects at the recommended Part B dose of 75 mg BID, the frequency of response and type of response according to IWG-MRT response criteria for subjects with MF will be evaluated. The frequency of disease assessment to treatment and type of response (e.g. every 2 months, and spleen volume) will be provided in a data listing by subject.

### **9.1.4 Chronic Lymphocytic Leukemia**

For cohorts that have at least 5 subjects at the recommended Part B dose of 75 mg BID, the frequency of response, and type of response according to the criteria of the International Workshop on Chronic Lymphocytic Leukemia, will be evaluated. For patients with persistent lymphocytosis, a partial response in all other measures will be defined as a partial response with lymphocytosis. Duration of response and the PFS rate at week 24 will also be evaluated.

### **9.1.5 Evaluation of Performance Status**

For cohorts that have at least 5 subjects at the recommended Part B dose of 75 mg BID, the ECOG performance status and the changes from baseline will be presented with frequency tables at each dose level.

The ECOG performance status will be assessed according to the Schedule of Assessments (see Section 3.2). ECOG scores – numeric scale, range from 0 to 5, inclusive – will correspond to the ECOG responses, as shown within Appendix B of the Study Protocol. For a given treatment window ECOG assessment, change from baseline (CFB) in ECOG will be calculated as the difference between the treatment window ECOG assessment and baseline ECOG (i.e., CFB in ECOG = treatment window ECOG – baseline ECOG).

Summaries for absolute and CFB in ECOG will be provided by visit and treatment cohort using frequencies (counts and percentages) for each study component separately and combined.

Absolute and CFB in ECOG will be provided in a data listing by subject.

### **9.2 Evaluation of Time to Treatment**

The time (days) on treatment, beginning with the date of first administration of study drug and ending with the date of discontinuation or completion of study treatment, will be provided by treatment cohort using descriptive statistics (n, mean, standard deviation, median, minimum, and maximum).

Time on treatment will be provided in a data listing by subject.

### **9.3 Evaluation of Time to Progression**

For cohorts that have at least 5 subjects at the recommended Part B dose of 75 mg BID, the time to disease progression (radiographic or clinical) will be calculated as the number of days from the date of the

first dose of study medication to the date the progression is observed or death due to tumor progression in the absence of previous documented PD. For subjects who have not progressed at the end of the study, the time to progression will be censored at the last assessment, unless the subject dies due to disease progression.

#### **9.4 Evaluation of Progression-free Survival**

For cohorts that have at least 5 subjects at the recommended Part B dose of 75 mg BID, PFS will be calculated as the number of days from the date of the first dose of study medication to the date progression is observed, or death from any cause. PFS will be analyzed using the Kaplan-Meier method.

#### **9.5 Exploratory Efficacy Variables**

##### **9.5.1 Panel of Biomarkers**

Serum concentrations of the biomarkers Phospho-S6, Phospho-STAT3, Phospho-SYK 525/526, Phospho-ERK, basal B-cell surface activation markers, CD69, CD88, and the panel of markers of inflammation (see Appendix C of the Study Protocol), including CRP,  $\beta$ 2-microglobulin, and IL-10, will be collected pre-dose on Day 1 of Cycle 1 (baseline assessment) and at the visits/timepoints indicated within the within the Schedule of Assessments (see [Section 3.2](#)). For each biomarker and post-baseline assessment, change from baseline (CFB) in the biomarker will be calculated as the difference between the post-dose assessment and the baseline value (i.e., CFB in biomarker = post-dose biomarker value – baseline biomarker value).

Summaries for absolute and CFB for each biomarker will be provided by visit/timepoint and treatment cohort using descriptive statistics (n, mean, standard deviation, median, coefficient of variance, minimum, and maximum).

Absolute and CFB for each biomarker will be provided in a data listing by subject.

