## **11.3 Exploratory Markers**

### **11.3.1 Assessment of Biomarkers**

A panel of biological markers will be assessed to determine the effect of ASN002 on both SYK and JAK/STAT pathways in the disease process. Biomarkers for this study are shown in **Table 9**. Some of these markers include the following:

Lymphomas and solid tumors, changes from baseline in the following biomarkers

- Phospho-STAT3, Phospho-S6, Phospho-SYK 525/526, Phospho-ERK
- DLBCL molecular subtype (GCB, ACB) (baseline only)
- Inflammation panel (**Appendix C**).

Myelofibrosis

- Changes in JAK (V617F) mutant allele burden.
- Inflammation panel (**Appendix C**).

CLL

- Changes in BCL2 expression
- Changes in the status of chromosome 17p.
- Inflammation panel (**Appendix C**).

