## **14 ASSESSMENT OF PHARMACODYNAMICS**

### **14.1 PD Sample Collection**

Blood samples will be collected according to the schedule in **Table 1- Table 4**, and analyzed to assess

- Inhibition of phosphorylation of S6, STAT3, SYKTyr525/526, and ERK;
- DLBCL molecular subtyping may be conducted on archived tumor if the subtyping has not been done as standard of care.
- Change from baseline in a panel of markers of inflammation (see **Appendix C**)
- Change from baseline in JAK (V617F) mutant allele burden in subjects with MF
- Change from baseline in BCL2 and chromosome 17p in subjects with CLL.

Due to specimen shipping considerations, only U.S. sites will collect PD samples to determine the inhibition of phospho-proteins.

Refer to the Study Laboratory Manual for further information regarding sample collection and shipments.

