### **2.3.1.3 Exploratory Efficacy Variables**

The exploratory pharmacodynamics variables for efficacy are:

- Inhibition of phosphorylation of S6, STAT3, SYK 525/526, and ERK.
- Inhibition of the basal B-cell surface activation markers, CD69 and CD88.
- Change from baseline in JAK (V617F) in ML patients.
- Change from baseline in BCL and chromosome 17p in CLL patients.
- Reduction of CRP,  $\beta$ 2-microglobulin, and IL-10.
- Change from baseline in a panel of markers of inflammation (see Appendix C of the Study Protocol for the panel of markers).

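### SAP 9.5.1 plans no relative measure of phosphorylation inhibition, labels every marker as a serum concentration, and lists two markers absent from the current protocol

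*SAP*

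**What the plan says.** SAP 2.3.1.3 lists among its exploratory variables "Inhibition of phosphorylation of S6, STAT3, SYK 525/526, and ERK" and, separately, "Inhibition of the basal B-cell surface activation markers, CD69 and CD88".

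SAP 9.5.1 is the analysis section for these variables. It opens with "Serum concentrations of the biomarkers Phospho-S6, Phospho-STAT3, Phospho-SYK 525/526, Phospho-ERK, basal B-cell surface activation markers, CD69, CD88", then adds the inflammation panel. The only derived quantity is the difference "CFB in biomarker = post-dose biomarker value – baseline biomarker value". Actual values and this difference are summarised by time point and treatment cohort (n, mean, SD, median, coefficient of variance, range) and listed by subject.

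Protocol 14.1 also speaks of inhibition of phosphorylation. It refers to blood samples without naming a matrix, and says of the phospho-protein samples that "only U.S. sites will collect PD samples to determine the inhibition of phospho-proteins". Protocol 11.3.1 puts the same four phospho-proteins under the line "Lymphomas and solid tumors, changes from baseline in the following biomarkers", and protocol 15.8 plans actual values and changes from baseline for all PD variables.

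SAP 14 states that the analysis plan makes no changes from the protocol. Protocol section 15 gives the SAP priority where the two differ.

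**The concern.** The variable is named as inhibition, but the derivation is a raw difference in assay units. Neither document gives a formula for inhibition. A reader of the tables would see a mean change that depends on how high each subject's baseline was. The proportion by which phosphorylation fell could not be read from it.

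Two smaller inconsistencies sit in the same section. A single serum label covers every marker, including ones the SAP calls surface markers. The section also includes markers that the current protocol does not list, while the SAP reports no departures.

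What is at stake is how clearly the SYK and JAK/STAT pathway effects can be read. Effects on these phospho-proteins head the list of exploratory objectives (protocol 7.3, SAP 2.1.3). The study is open-label, so a relative measure chosen after the data have been seen would be a post hoc choice.

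**Working it through.** The plan states no figure on this point, so there is nothing to reproduce. The check is a comparison of text plus an illustration on assumed values, because the documents give no assay data.

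**Variable against derivation**
- Named variable: inhibition (SAP 2.3.1.3, protocol 14.1).
- Derived quantity: post-dose minus baseline (SAP 9.5.1). SAP 7.3 has the same default.
- A percentage, ratio or other definition of inhibition: none in SAP 2.3.1.3, 7.3 or 9.5.1.

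**Illustration (all baselines and post-dose values assumed)**

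Change = post-dose - baseline. Percent inhibition = 100 x (1 - post-dose/baseline).

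1. The same change can mean different inhibition. A change of -50 units is 100 x (1 - 10/60) = 83.3% from baseline 60, 100 x (1 - 50/100) = 50% from baseline 100, and 100 x (1 - 350/400) = 12.5% from baseline 400.
2. The same inhibition can give different changes. Two subjects go from 200 to 100 and from 20 to 10. The changes are -100 and -10, with mean -55 and SD = 90/√2 = 63.6. Percent inhibition is 50% in both. Both log ratios are ln(0.5), so the geometric mean ratio is 0.5 with no spread.
3. Four subjects with baselines 60, 100, 400 and 1000 and 50% inhibition in each give changes of -30, -50, -200 and -500. The mean is -195 and the SD is 217.
4. The effect depends on how far baselines differ. For two subjects with equal 50% inhibition and baselines in ratio k, the SD of the change divided by the size of its mean is √2 x (k - 1)/(k + 1). This is 0 at k = 1, 0.47 at k = 2 and 1.16 at k = 10 (the last matches 63.6/55). With equal baselines the two measures agree; the gap grows with baseline spread.

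**Number of subjects.** Part A has up to 6 subjects per dose level (protocol synopsis). Phospho-protein samples come only from U.S. sites (protocol 14.1) or, in Part B, from selected sites (footnote to the PK/PD assessment table). One subject with a high baseline can therefore weigh heavily on a cohort mean.

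**Matrix.** SAP 9.5.1 says serum for all markers. Protocol 14.1 says only "Blood samples will be collected according to the schedule in" the tables, without a matrix per assay. Among PD markers, the protocol uses the word serum only for inflammation biomarkers (6.4.3). Assay details are left to the Laboratory Manual, which is not among the documents.

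**Marker lists.** CD69 and CD88 appear in SAP 2.3.1.3 and 9.5.1. Neither appears in the protocol's current PD lists: synopsis, 7.3, 11.3.1, Table 9, 14.1 and Appendix C. The amendment summary, used here only as background, records that assays for CD69 and CD86 were dropped. CD88 is named nowhere in the protocol.

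**The case against.** The strongest reply is that SAP 9.5.1 does what the protocol asks. Protocol 11.3.1 and 15.8 plan change from baseline, and the protocol synopsis defines the PD population by having a determined change. The objective is to evaluate effects, and a negative change is a reduction. Baseline and post-dose values are listed per subject, so percent inhibition can be derived later. A separate population PK/PD plan is announced (SAP 11.2, protocol 15.7.2) and might define it.

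Most of this stands. A reader might infer that inhibition is never computed. The documents do not support that: an absolute reduction is computed, and the unseen PK/PD plan cannot be ruled out. What remains is that this SAP neither defines inhibition nor plans a relative summary, and nothing supplied commits the other plan to doing so.

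Three further inferences should also be resisted:
- **The CD markers have no data.** Some of the 40 Part A subjects enrolled before this amendment may have CD69 or CD86 results, and CD88 may be a slip for CD86.
- **Serum is proven wrong for the phospho-proteins.** Without the Laboratory Manual it is only doubtful. The label is plainly awkward for markers described as surface markers.
- **The Part B dose rests on these outputs.** The amendment rationale mentions PD in general terms, but the only PD evidence in protocol 6.4.3 is the inflammation biomarkers.

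The illustration is constructed, and its size depends on baseline spread that the documents do not give.

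**Conclusion.** The point holds as a minor one. This SAP calls the phospho-protein variable inhibition but plans only actual values and an arithmetic difference. In cohorts of up to 6 with differing baselines, that summary does not show proportional inhibition. The distortion runs from none with equal baselines to a mean of -55 with SD 63.6 for two subjects who both have 50% inhibition from a tenfold baseline difference. These are assumed values, not estimates for this assay.

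The blanket serum label and the listing of CD69 and CD88 are inconsistencies of text. On the two markers, the declaration of no changes in SAP 14 is not accurate.

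The severity stays low because the variables are exploratory and descriptive, with no hypothesis test or decision rule attached.

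**What to change.** 1. In SAP 9.5.1, keep the actual values and change from baseline, which follow protocol 15.8. For Phospho-S6, Phospho-STAT3, Phospho-SYK 525/526 and Phospho-ERK, add percent inhibition = 100 x (1 - post-dose/baseline). Summarise it as a log ratio (geometric mean ratio) by time point and dose level, with a stated rule for zero or below-limit values.
2. State matrix and unit for each assay as given in the Laboratory Manual, and keep the term serum concentrations only where it applies.
3. Confirm whether CD88 is an error for CD86. Then delete the surface markers from SAP 2.3.1.3 and 9.5.1, or limit them to subjects with data from earlier protocol versions.
4. Record the resulting difference from the protocol in SAP 14.

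The cost is SAP wording, one extra derivation and one handling rule. No new samples or visits are needed, and limiting rather than deleting the surface markers avoids discarding data already collected.

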### **10 SAFETY ANALYSIS**

Unless stated otherwise, all safety analyses will be performed on the Safety Population.

#### **10.1 Adverse Events**

Treatment emergent adverse events (TEAE) will be classified into a standardized terminology using the Medical Dictionary for Regulatory Activities (MedDRA, version 17.0 or higher) system organ classifications and preferred terms. All summaries of the incidence of treatment-emergent adverse events will be provided using the Safety Population by treatment cohort and overall. Although a preferred term or system organ class may be reported more than once for a subject, each subject will only be counted once in the incidence count for that preferred term or system organ class. Summaries of the following types will be provided:

- Summary of treatment-emergent adverse events;
- Summary of treatment-emergent adverse events by MedDRA system organ class and MedDRA preferred term;
- Summary of treatment-emergent adverse events by MedDRA system organ class, MedDRA preferred term, relationship to study drug, and intensity;

- Summary of serious treatment-emergent adverse events leading to discontinuation from the study by MedDRA preferred term, sorted alphabetically by system organ class and preferred term;
- Summary of treatment-emergent adverse events leading to discontinuation from the study by MedDRA preferred term, sorted alphabetically by system organ class and preferred term.

These summaries will present the number and percentage of subjects reporting an adverse event for each classification level. The denominators for calculating the percentages will be based on the number of exposed subjects in the Safety population (i.e., study drug was administered) in the treatment cohort summarized.

Listing of subject dropouts due to AEs prior to post-dose tumor assessment will be generated. All adverse events, serious adverse events and deaths, and adverse events leading to discontinuation from the study will also be provided in data listings by subject.

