### **9.3 Subject Discontinuation Criteria**

Study discontinuation will occur when a subject who signed informed consent ceases participation in the study. Subjects can be discontinued from the study for one of the following reasons:

- An adverse event;
- Progression of disease;
- Death;
- A protocol violation (reason must be specified, for example: lack of compliance, use of a prohibited concomitant medication, failure to meet inclusion/exclusion criteria after study entry, etc.);
- Withdrawal of consent by the subject (reason must be specified);
- The subject was “lost to follow-up”;
- Other reasons (reason must be specified, for example: the subject moved, investigator decision, sponsor decision to terminate study, etc.).

A subject is free to withdraw his consent and discontinue participation in the study at any time. The investigator must withdraw any subject from the study if the subject requests to be withdrawn. Any subject who withdraws consent as a result of an adverse event, regardless of intensity or investigator's opinion, must be reported as a discontinuation due to adverse event.

If a subject discontinues from the study, all end of treatment procedures should be conducted as detailed in **Table 1** or **Table 2**. The date a subject discontinues ASN002, and the reason for discontinuation will be recorded in the source documentation and electronic Case Report Form (eCRF). If a subject has an ongoing adverse event, the event will be followed until resolution or stabilization for at least 30 days after the last dose of ASN002. If a subject refuse to complete any of the specified End of Treatment procedures, this information will be recorded in the source documentation. A subject who discontinues from the study will not be allowed to re-enter the study.

When a subject is “lost to follow-up” (i.e., fails to return for study visits), a reasonable effort will be made to contact the subject:

1. to determine the reason for the failure to return and these contacts will be recorded in the source documents;
2. to follow up on any ongoing AEs from the previous visits;
3. to recover any unused ASN002.

The subject should be identified as “lost to follow up” in the eCRF, as appropriate.

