## 15 STATISTICAL CONSIDERATIONS AND METHODS

This section outlines the statistical methodology and principles which will be used for data analysis in this study. A separate statistical analysis plan (SAP) will further describe the details regarding statistical methods and will govern the analysis. Where differences occur between the protocol and the SAP, the SAP will take priority.

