### **15.3 Subject Disposition**

The number and percentage of subjects included in each study population will be summarized by dose level and overall. Subjects excluded from the safety and efficacy (EP or PP) populations or PK populations will be listed by dose level.

The number and percentage of subjects completed and discontinued during the treatment periods will be presented for each dose level and overall. Reasons for discontinuation from the treatment period as recorded on the eCRF will be summarized (number and percentage) by dose level and overall for all treated subjects.

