The incidence of TEAEs by severity and relationship to study drug will be summarized by system organ class, preferred term, and dose level. If more than 1 AE is coded to the same preferred term for the same subject, the subject will be counted only once for that preferred term using the most severe and most related occurrence for the summarization by severity and by relationship to the study drug respectively. The incidence of TEAEs will also be summarized by preferred term and dose level and sorted by decreasing frequency. SAEs and AEs leading to premature discontinuation of study drug will be summarized by preferred term and dose level, and sorted by decreasing frequency for dose level.

Listings will be presented for subjects with AEs, subjects with SAEs, subjects with AEs leading to discontinuation, and death. All safety summaries will be performed by dose level and Parts A, and B, separately and combined, if appropriate.

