### **8.2 Subject Disposition**

Subject disposition will be summarized by treatment cohort and overall. The number and percentage of subjects who are still on treatment on this study or who have rolled over to the extension study, and the number and percentage of subjects discontinued from the study will be presented by reason for discontinuation. The denominators for calculating the percentages will be based on the number of subjects in the analysis population by treatment cohort and overall.

Discontinued subjects will be provided in a data listing by subject.

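### SAP 10.1 limits its only specified serious-event table to events leading to discontinuation, whereas the protocol promises SAE incidence at each dose level

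*SAP*

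**What the plan says.** **Protocol.** The Safety Analyses part of the synopsis names three things to be assessed at each dose level: incidence of AEs, AEs resulting in discontinuation, and SAEs. It then says that SAEs and AEs resulting in discontinuation get separate summaries. Section 15.5.4 says, twice, that "SAEs and AEs leading to premature discontinuation of study drug will be summarized by preferred term and dose level". Its listing sentence names subjects with SAEs and subjects with AEs leading to discontinuation as separate items. For disposition, section 15.3 says "Reasons for discontinuation from the treatment period as recorded on the eCRF will be summarized (number and percentage) by dose level and overall". Section 9.3 states "Study discontinuation will occur when a subject who signed informed consent ceases participation in the study" and, further on, "The date a subject discontinues ASN002, and the reason for discontinuation will be recorded in the source documentation" and in the eCRF.

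**SAP.** Section 10.1 specifies five TEAE summaries:
- overall;
- by system organ class and preferred term;
- the same, split by relationship and intensity;
- serious TEAEs that led to discontinuation from the study;
- all TEAEs that did so: "Summary of treatment-emergent adverse events leading to discontinuation from the study by MedDRA preferred term".

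It also plans by-subject listings of all AEs, of SAEs and deaths, and of AEs that led to leaving the study. Section 8.2 says "the number and percentage of subjects discontinued from the study will be presented by reason for discontinuation".

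**Which governs.** Protocol section 15: "Where differences occur between the protocol and the SAP, the SAP will take priority". SAP section 14 says that nothing was changed.

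**The concern.** Safety and tolerability are primary objectives in both parts, and the proportion of subjects with a serious event at each dose is a basic safety result. As written, the SAP specifies a table for one subset of serious events, those that ended participation. An SAE that resolved and allowed the subject to continue, or that occurred in a subject who left for progression, falls outside it. No other specified table separates serious from non-serious events. The table by intensity does not do so, because CTCAE grade and seriousness are different classifications.

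The serious-event summary that a programmer builds from the SAP would therefore answer a narrower question than the protocol asks. A reader told that nothing changed could take it for the full SAE incidence.

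The same bullets refer to leaving the study where protocol section 15.5.4 refers to stopping study drug, and SAP 8.2 differs from protocol 15.3 in the same way. That is an inconsistency of wording between the two documents.

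**Working it through.** The plan gives no figure to reproduce. The check has two parts.

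**1. Size of the gap for serious events.** Inputs, all from protocol section 6.3 (Part A, cut-off 09 February 2017): 27 treated; 21 discontinued treatment; 13 of those 21 for progression; 11 with at least one SAE.

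- Still on treatment: 27 − 21 = 6.
- Stopped for a recorded reason other than progression: 21 − 13 = 8, and 8/27 = 29.6%.
- Could not appear in a discontinuation table by recorded reason: 6 + 13 = 19.
- Patients with an SAE: 11/27 = 40.7%.
- Fewest SAE patients outside the table: 11 − 8 = 3, reached only if all 8 stopped because of an SAE. Section 6.3 does not give the reasons for those 8.
- Most outside the table: 11, if none of the 8 stopped because of an SAE.

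On these data the SAP table would show between 0 and 8 patients (0% to 29.6%), against an SAE incidence of 40.7%. In a Part B cohort of 14, each subject whose SAE did not lead to discontinuation lowers the tabulated rate by 1/14 = 7.1 percentage points.

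**2. Which event each summary uses.**

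| Summary | Protocol | SAP |
|---|---|---|
| Serious events | all SAEs, per dose level (synopsis) | only those leading to discontinuation from the study (10.1) |
| AEs leading to discontinuation | of study drug (15.5.4) | from the study (10.1, table and listing) |
| Reasons for discontinuation | from the treatment period (15.3) | from the study (8.2) |
| Time on drug and exposure | duration (15.5.2, 15.6.2) | duration and dose, no reason (9.2, 10.2) |

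Row 1 differs in substance. Rows 2 and 3 differ in wording, and whether the counts differ depends on how the two terms are used in practice.

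**The case against.** **The SAP follows section 15.5.4.** The phrase about SAEs and AEs leading to premature discontinuation can be parsed so that the qualifier applies to both, which would yield the SAP's bullet. The wording allows that reading. However, the opening sentence of the synopsis safety text names SAE incidence per dose level without that qualifier, and the listing sentence in 15.5.4 separates subjects with SAEs from subjects whose AEs led to discontinuation. The broader reading is the one consistent with the whole protocol.

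**Nothing is lost.** All SAEs are listed by subject, cohorts are small, and the overall TEAE summary might carry a row for serious events. The first two points are true and limit the consequence. The third is possible, but the SAP specifies no such row.

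**No decision depends on it.** Dose escalation rests on DLTs and the safety review committee, and these tables are descriptive. That also stands, and it makes this a reporting matter.

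**A stronger reading that a reader might infer.** Because SAP 10.1 and 8.2 refer to leaving the study, one could conclude that subjects who stop ASN002 for toxicity will be undercounted. The documents do not show this:
- SAP 8.2 sets subjects still on treatment, or rolled over to the extension, against those discontinued from the study. That scheme works only if the last group means treatment stop.
- Protocol 9.3 runs the two terms together, describes one recorded reason, and says that a consent withdrawal caused by an AE "must be reported as a discontinuation due to adverse event".
- In Part A, a Cycle 1 DLT means discontinuation from the study, as does a later AE meeting DLT criteria that recurs or does not resolve in time (8.3.3).
- After the last dose there is only an end-of-treatment visit and a 30-day visit, and the latter has no disease assessment.

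The Part B rule on recurrent toxicity does refer to stopping study treatment, so the counts could differ in principle. The documents give no evidence that they would.

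**Conclusion.** The point holds for serious events. The SAP's only specified serious-event table is narrower than the protocol's commitment, and SAP section 14 does not disclose this. On the February 2017 Part A data, at least 3 of the 11 patients with an SAE, and possibly all 11, would be missing from it, although all remain in the SAE listing.

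The minimum of 3 rests on three assumptions:
- Entry to the table follows the recorded reason for stopping. If it follows a field on the AE page, a patient recorded as stopping for progression might also be flagged and the minimum could be smaller. The CRF is not shown.
- Reasons for stopping treatment, which section 6.3 reports, stand in for reasons for leaving the study.
- The 11 SAEs were treatment-emergent, which section 6.3 does not say.

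The contrast between study and study drug in SAP 10.1 and 8.2 is a real inconsistency with protocol 15.5.4 and 15.3, but an undercount of drug discontinuations is not demonstrated and may be zero.

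**What to change.** In SAP 10.1, change the serious-event bullet to a summary of all serious TEAEs by system organ class, preferred term and treatment cohort, removing the restriction to discontinuations.

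In the same edit, for consistency with the protocol:
- in SAP 10.1, key the remaining discontinuation summary and the matching listing to permanent discontinuation of ASN002;
- in SAP 8.2, present reasons for permanent discontinuation of ASN002, in line with the treatment-period reasons in protocol 15.3.

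Both can use the stop reason that protocol 9.3 already requires.

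The cost is a few lines of SAP text and a broader version of a table already planned. No new data are needed: SAEs are already collected and listed, and treatment-stop reasons have already been reported in protocol section 6.3. The serious-event table will show more subjects than the present wording would allow. SAP section 14 would then be accurate as to which events these summaries cover.
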